## Appendix 2. Hepatitis B Testing Algorithm and Full Eligibility Criteria

All subjects will undergo screening for hepatitis B for eligibility (See [Appendix 5.1](#) for Japan-specific requirements).

**For subjects in countries in which hepatitis B prevalence has been reported at a rate of >5.0%\* or if required by local standard of care, subjects will be tested as follows:**

1. At screening, HBsAg and HBcAb will be tested:
  - a. If both tests are negative, the subject is eligible for study inclusion.
  - b. If HBsAg is positive, the subject must be excluded from participation in the study.
  - c. If HBsAg is negative and HBcAb is positive, HBsAb and HBVDNA reflex testing is required:
    - i. If HBsAb is negative, the subject must be excluded from participation in the study;
    - ii. If HBV DNA is detected, the subject must be excluded from participation in the study;
    - iii. If HBsAb is positive and HBV DNA is undetectable, the subject is eligible for study inclusion. If the subject is included in the study, for subsequent visits HBVDNA testing must be performed according to the [Schedule of Activities](#).

**For subjects in all other countries, subjects will be tested as follows:**

1. At screening, HBsAg and HBcAb will be tested:
  - a. If both tests are negative, the subject is eligible for study inclusion.
  - b. If HBsAg is positive, the subject must be excluded from participation in the study.
  - c. If HBsAg is negative and HBcAb is positive, HBsAb reflex testing is required:
    - i. If HBsAb is negative, the subject must be excluded from participation in the study;
    - ii. If HBsAb is positive, the subject is eligible for study inclusion. If the subject is included in the study, for subsequent visits no hepatitis B testing is required.

\* The Polaris Observatory Collaborators. Global prevalence, treatment, and prevention of hepatitis B virus infection in 2016: a modelling study. *Lancet Gastroenterol Hepatol.* 2018;3(6): 383-403.

### Appendix 3. Guidelines for Subject Safety Monitoring and Discontinuation

These guidelines for subject safety monitoring and discontinuation are to be applied to all subjects in study B7981015. Additional individual subject monitoring is at the discretion of the investigator and dependent on any perceived safety concerns. Unscheduled clinical labs may be obtained at any time during the study to assess such concerns, and a subject may be withdrawn at any time at the discretion of the investigator.

#### Appendix 3.1. Monitoring

All potential treatment-related events of rash will be followed up until resolution or agreement with Pfizer.

**The following laboratory abnormalities require re-testing until resolution or agreement with Pfizer:**

Laboratory Variable	Laboratory Value	Re-testing Timeframe a
Hematology		
Absolute Neutrophil Count	<1000/mm  (<1.0 × 10  /L)	Within 1 week
Hemoglobin	<10.0 g/dL (<6.21 mmol/L or <100 g/L) OR Decrease of ≥2.0 g/dL from baseline	Within 1 week
Platelet count	<100,000/mm  (<100.0 × 10  /L)	Within 1 week
Absolute Lymphocyte Count b	<600/mm  (<0.6 × 10  /L)	Within 1 week
Serum Chemistry		
Creatine kinase c	>3 × ULN	Within 1 week
Aspartate aminotransferase	See Section 8.4.2 for potential cases of drug-induced liver injury.	Within 48 hours
Alanine aminotransferase	See Section 8.4.2 for potential cases of drug-induced liver injury.	Within 48 hours
Total bilirubin	See Section 8.4.2 for potential cases of drug-induced liver injury.	Within 48 hours

- Based on awareness of the abnormal results.
- Subjects with absolute lymphocyte count <500/mm^3 (0.5 × 10^9/L) will be reflex-tested for FACS-TBNC until the absolute lymphocyte count resolves or stabilizes at a level acceptable to the investigator and sponsor.
- In addition to re-testing creatine kinase >3 × ULN, urine myoglobin will be performed as reflex testing for any subject with creatine kinase >10 × ULN.

In case of positive urine pregnancy test, the subject will have study drug interrupted and a serum sample collected on the same day (or as soon as possible) and submitted to the central laboratory for pregnancy testing.

## Appendix 3.2. Discontinuation

**Treatment will be discontinued, and the subject withdrawn from this study following completion of the Early Termination visit and the Follow-up Visit (whenever possible) for:**

### Adverse Events:

- Serious infections, defined as any infection (viral, bacterial, and fungal) requiring parenteral antimicrobial therapy or hospitalization for treatment or meeting other criteria that require the infection to be classified as serious adverse event;
- Treatment-related SAEs;
- Clinically meaningful, treatment-emergent declines in hearing from baseline (refer to Audiometry Study Guide for details) are to be discussed with the Sponsor for possible withdrawal from the study;
- Other serious or severe AEs, at the discretion of the investigator or sponsor.

### ECG Findings:

- Confirmed QTcF >500 milliseconds;
- Confirmed increase from baseline in QTcF of >60 milliseconds.

### Investigational Product Interruptions:

- Subjects interrupting investigational product for more than 10 days between visits are to be discussed with the sponsor for possible withdrawal from the study.

### Laboratory Abnormalities:

All the following laboratory abnormalities **require discontinuation** if they are confirmed by re-test. Refer to the associated re-testing timeframes for laboratory abnormalities in [Appendix 3.1](#):

- Absolute Neutrophil Count <750/mm^3 (<0.75 × 10^9/L).
- Hemoglobin <9.0 g/dL (<5.59 mmol/L or <90 g/L) or a decrease of >30% from baseline (either criterion or both).
- Platelet count <75,000/mm^3 (<75.0 × 10^9/L).
- Absolute Lymphocyte Count <500/mm^3 (<0.5 × 10^9/L).

NOTE: Subjects with absolute lymphocyte count <500/mm^3 (0.5 × 10^9/L) will be reflex tested for FACS-TBNK until the absolute lymphocyte count resolves or stabilizes at a level acceptable to the investigator and sponsor.

- Creatine kinase  $>10 \times$  ULN.

NOTE: In addition to re-testing creatine kinase  $>3 \times$  ULN, urine myoglobin will be performed as reflex testing for any subject with creatine kinase  $>10 \times$  ULN.

- Aspartate aminotransferase (AST) or alanine aminotransferase (ALT) that meet ANY of the following:
  - $>3$  times the upper limit of normal with at least one total bilirubin value  $>2$  times the upper limit of normal;
  - $>3$  times the upper limit of normal accompanied by signs or symptoms consistent with hepatic injury (eg, new onset elevated PT/INR);
  - Two sequential AST or ALT elevations  $>5$  times the upper limit of normal, regardless of total bilirubin or accompanying signs or symptoms.

NOTE: In each case, there is a need for additional investigations, such as review of ethanol, recreational drug and dietary supplement consumption; testing for acute hepatitis A, B or C infection and biliary tract imaging should be promptly discussed with the sponsor or designee.

#### **Pregnancy:**

- Female subjects confirmed as pregnant during the study (see [Section 8.4.3.1](#)).

#### **Prohibited Medications:**

- Subjects who are treated with any prohibited medication during the course of the study may require discontinuation. Subjects who are administered a prohibited medication are to be discussed with the sponsor for possible withdrawal from the study.

#### **Suicidal Ideation:**

- Subjects with a “yes” answer on items 4, 5, or on any question in the suicidal behavior section of the C-SSRS must be discontinued. The subject must be referred to a mental health professional for appropriate evaluation and treatment. If the subject cannot be seen by a mental health professional within 24 hours, then the subject should be sent to a local emergency room for psychiatric assessment.

#### **Discontinuation/End of Treatment Monitoring:**

Any subject meeting discontinuation criteria must enter into the Follow-up Period with their first follow-up visit occurring 1 week after their last dose whenever possible, until the event has returned to normal or baseline levels or is deemed clinically stable. The procedures scheduled for Early Termination Visit will be performed on the last day the subject takes the investigational product or as soon as possible thereafter. The only exception to this is when a subject specifically withdraws consent for any further contact with him or her or persons previously authorized by the subject to provide this information. Additional follow-up visits may occur as needed until any clinically relevant abnormalities or adverse events have resolved, returned to a baseline state, or are deemed clinically stable.

## Appendix 4. Prohibited and Permitted Concomitant CYP3A Inducers and Substrates

Please note that this list addresses only CYP3A inducers and CYP3A substrates. Other prohibited medications for this trial are listed in [Section 5.8.2](#). Refer to [Section 5.8.1](#) for additional information regarding permitted medications for this trial, including CYP3A inhibitors.

This is not an all-inclusive list. Study personnel should stay current and consult with their pharmacy to exclude all concomitant medications that are moderate to potent CYP3A inducers or sensitive or moderate sensitive CYP3A substrates. If a medication is a sensitive or moderate sensitive CYP3A substrate and is not listed below as prohibited or permitted, consultation with the Sponsor is required.

### Appendix 4.1. Prohibited Concomitant CYP3A Inducers and Substrates

Sensitive CYP3A Substrates##	Moderate Sensitive CYP3A Substrates§	Moderate to Potent CYP3A Inducers**
Dasatinib	Aprepitant	Avasimibe#
Dronedarone	Eliglustat	Bosentan
Ebastine	Pimozide	Barbiturates
Lomitapide	Rilpivirine	Carbamazepine#
Nisoldipine		Efavirenz
Sirolimus		Etravirine
Tacrolimus		Mitotane#
Tolvaptan		Modafinil
		Nafcillin
		Phenobarbital#
		Phenytoin#
		Rifabutin#
		Rifampin #
		St. John's Wort#
		Talviraline

\*\* All prohibited drugs that are CYP3A inducers require at least a 28 day or 5 half-lives (whichever is longer) washout prior to the first dose of study intervention.

**In a situation where appropriate medical care of a participant requires the use of a prohibited CYP3A inducer:** Moderate to potent inducers of CYP3A are not permitted in the study EXCEPT in emergency situations. *Note: Mitotane is not permitted for any duration due to its long half-life; however, if necessary mitotane may be used in an emergency, however the participant will then be discontinued from the study.* Topical (including skin or mucous membranes) application of antimicrobial and antifungal medications is permitted.

# Notated as potent inducers.

## Sensitive CYP3A substrates are drugs that demonstrate an increase in concentration-time curve (AUC) of  $\geq 5$ -fold with strong index inhibitors of a given metabolic pathway in clinical drug-drug interaction (DDI) studies.

§ Moderate sensitive substrates are drugs that demonstrate an increase in AUC of  $\geq 2$  to  $< 5$ -fold.

#### Appendix 4.2. Permitted Concomitant CYP3A Substrates

Sensitive CYP3A Substrates##		Moderate Sensitive CYP3A Substrates§
Alfentanil	Midazolam	Alprazolam
Avanafil	Naloxegol	Atorvastatin
Buspirone	Quetiapine	Colchicine
Darifenacin	Sildenafil	Rivaroxaban
Eletriptan	Simvastatin	Tadalafil
Eplerenone	Ticagrelor	
Felodipine	Triazolam	
Lovastatin	Vardenafil	
Lurasidone		

## Sensitive CYP3A substrates are drugs that demonstrate an increase in concentration-time curve (AUC) of  $\geq 5$ -fold with strong index inhibitors of a given metabolic pathway in clinical drug-drug interaction (DDI) studies.

Topical (including skin or mucous membranes) application of antimicrobial and antifungal medications is permitted.

§ Moderate sensitive substrates are drugs that demonstrate an increase in AUC of  $\geq 2$  to  $< 5$ -fold.

## Appendix 5. Country-specific Requirements

### Appendix 5.1. Japan-Specific Requirements for Hepatitis B Testing

1. At screening, HBsAg, HBcAb, and HBsAb will be tested for all subjects in Japan:
  - a. If all three tests are negative, the subject is eligible for study inclusion.
  - b. If HBsAg is positive, the subject must be excluded from participation in the study.
  - c. If HBsAg is negative, HBcAb is positive, and HBsAb is negative, the subject must be excluded from participation in the study.
  - d. If HBsAg is negative, HBcAb is negative, HBsAb is positive, and prior HBV vaccination is unequivocally documented, the subject is eligible for the study and does not require HBVDNA monitoring during the study.
  - e. If HBsAg is negative, HBcAb is negative, HBsAb is positive, and no unequivocal documentation of prior HBV vaccination is available, the subject is required to undergo HBVDNA reflex testing:
    - i. If HBVDNA is detected, the subject must be excluded from participation in the study;
    - ii. If HBVDNA is undetectable, the subject is eligible for study inclusion. If the subject is included in the study, for subsequent visits HBVDNA testing must be performed according to the [Schedule of Activities](#).
  - f. If HBsAg is negative, HBcAb is positive, and HBsAb is positive, the subject is required to undergo HBVDNA reflex testing:
    - i. If HBVDNA is detected, the subject must be excluded from participation in the study;
    - ii. If HBVDNA is undetectable, the subject is eligible for study inclusion. If the subject is included in the study, for subsequent visits HBVDNA testing must be performed according to the [Schedule of Activities](#).

## **Appendix 6. Alternative Measures During Public Emergencies**

The alternative study measures described in this section are to be followed during public emergencies, including the COVID-19 pandemic. This appendix applies for the duration of the COVID-19 pandemic globally and will become effective for other public emergencies only upon written notification from Pfizer. NOTE: Any deviations from the [Schedule of Activities](#) or the protocol (eg, missed or partially completed procedures or assessments) must be reported to the Sponsor in a timely manner and will be reported by the Sponsor as a protocol deviation.

Procedures which are missed due to COVID-19 disruptions are required to be performed at the next available opportunity, even if outside of a protocol-specified visit window.

Use of these alternative study measures are expected to cease upon the return of business as usual circumstances (including the lifting of any quarantines and travel bans/advisories).

### **Appendix 6.1. Eligibility**

While severe acute respiratory syndrome coronavirus 2 (SARS-CoV2) testing is not mandated for this study, local clinical practice standards for testing should be followed. A subject should be excluded if he/she has a positive test result for SARS-CoV2 infection, is known to have asymptomatic infection, or is suspected of having SARS-CoV2. Subjects with active infections are excluded from study participation per Exclusion #16. When the infection resolves, the patient may be considered for re-screening. In addition, the following criteria apply:

The subject must be able to perform all Screening and Day 1 procedures per the [Schedule of Activities](#) at the study site and/or designated ancillary facility (eg, for audiological evaluations and chest radiographs) in order to determine whether the subject meets eligibility criteria for the study. This includes collection and resulting of laboratory assessments through the central laboratory vendor.

The subject must meet eligibility criteria for the study.

It must be anticipated that the subject will be able to have the Week 2 and Week 4 safety laboratory tests collected/performed at the study site or an alternative clinical laboratory facility according to the windows in [Appendix 6.3](#)

If a subject does not meet the criteria described above, the subject cannot be enrolled in the study.

## Appendix 6.2. Telehealth Visits

In the event that in-clinic study visits cannot be conducted, every effort should be made to follow up on the safety of study subjects at scheduled visits per the [Schedule of Activities](#) or unscheduled visits. Telehealth visits may be used to continue to assess subject safety and collect data points. Telehealth includes the exchange of healthcare information and services via telecommunication technologies (eg, audio, video, video-conferencing software) remotely, allowing the subject and the investigator to communicate on aspects of clinical care, including medical advice, reminders, education, and safety monitoring. The following assessments must be performed during a telehealth visit:

Review dosing logs and record investigational product, including doses taken and any interruptions in intake of investigational product (ie, missed doses) since the last contact, and calculate compliance.

Review and record any AEs and SAEs since the last contact. Refer to [Section 8](#).

Review and record any new concomitant medications or changes in concomitant medications since the last contact.

For WOCBP: Review and record contraceptive method and results of pregnancy testing. Confirm that the subject is adhering to the contraception method(s) required in the protocol [Section 4.3.1](#). Refer to [Section 7.2](#) of the protocol and [Appendix 6.3](#) regarding pregnancy tests.

For premenarchal female subjects: Check for initiation of menarche.

Collection of updated audiological history (Part 1 in the Audiometry Study Guide Worksheet for Post Day 1 visits) at visits requiring audiological evaluation.

Body temperature and collection method (eg, oral, tympanic, axillary), pulse rate, and respiratory rate (measured by study subject/caregiver).

Administration of the C-SSRS performed by a qualified rater. Per [Section 7.7.1](#), if there are “yes” answers on items 4 or 5 of the suicidal ideation section or on any question in the suicidal behavior section of the C-SSRS, the subject will be discontinued from the study and referred to a mental health professional for appropriate evaluation and treatment.

NOTE: If the investigator determines that additional evaluation is warranted based on the information collected during the remote visit described above, follow-up is required to be performed, with results submitted to and reviewed by the investigator prior to shipping investigational product to the subject.

Study subjects must be reminded to promptly notify site staff about any change in their health status.

## Appendix 6.3. Alternative Facilities for Safety Assessments

### Laboratory Testing

With the exceptions noted in [Appendix 6.1](#) for Screening and Day 1, if a study subject is unable to visit the site for protocol-specified safety laboratory evaluations, testing may be conducted at a local laboratory if permitted by local regulations. The local laboratory may be a standalone institution or within a hospital. Collection of blood and urine samples may also be performed at the subject's home per [Appendix 6.5](#). The following safety laboratory evaluations may be performed at a local laboratory or in the subject's home:

Hematology;

Serum chemistry;

Fasting lipid panel;

Urinalysis;

Pregnancy testing (for WOCBP);

Refer to the [Schedule of Activities](#) for visits at which these tests are required and to [Section 7.5.7](#) for additional details regarding these tests.

If it is not possible for the subject to have the above tests completed within the visit window specified in the [Schedule of Activities](#), an extended window may be allowed to collect samples for these laboratory tests, provided that the investigator has performed the remote visit as described above, assessed each case, and determined that it would not increase risk to a subject. The extended windows for laboratory sample collection for each study visit are noted in [Table 8](#). These windows apply only to laboratory samples collected during interruptions due to public emergencies, including the COVID-19 pandemic, based upon written notification from Pfizer. If the laboratory samples are not collected within the specified extended window for the visit, the subject must temporarily withhold investigational product until the required laboratory samples can be collected.

If a local laboratory is used, qualified study site personnel must order, receive, and review results. Site staff must collect the local laboratory reference ranges and certifications/accreditations for filing at the site. Laboratory test results are to be provided to the site staff as soon as possible and must be received and reviewed by the investigator within 14 days after they are collected in order to determine eligibility to continue dosing. In addition, laboratory test results from the previous visit must be available and reviewed by the investigator prior to shipping investigational product at the current visit. The local laboratory reports must be filed in the subject's source documents/medical records. Relevant data from the local laboratory report must be recorded on the CRF.

Special attention should be paid to ensure that laboratory results are checked against the Guidelines for Subject Safety Monitoring and Discontinuation in [Appendix 3](#) and that required follow-up is performed as applicable.

If a subject requiring pregnancy testing cannot visit a local laboratory for pregnancy testing, a home urine pregnancy testing kit with a sensitivity of at least 25 IU/mL may be used by the subject to perform the test at home, if compliant with local regulatory requirements. Urine pregnancy test results may be collected based on information provided by the subject (or their legally authorized representative, if appropriate) during the remote visit. **The urine pregnancy test result must be available prior to dispensing or shipping investigational product to a subject.** The pregnancy test outcome must be documented in the subject's source documents/medical records and relevant data recorded on the CRF. Confirm that the subject is adhering to the contraception method(s) required in the protocol.

**NOTE:** Pregnancy testing (for WOCBP) between the Week 40 and 48 visits (at approximately Week 44) and study site contact with subjects to obtain pregnancy test results is required for WOCBP in VHP countries outlined in the [Schedule of Activities](#) and [Section 7.2](#).

**Table 8. Windows for Remote Visits and Laboratory Sample Collections if Required Due to Disruptions from Public Emergencies**

Visit (Day in Study)	Remote Visit Window (Day in Study) a	Lab Collection Window (Day in Study) b
Week 2 (Day 15)	±3 days (Day 12-18)	±3 days (Day 12-18)
Week 4 (Day 29)	±3 days (Day 26-32)	-3/+7 days (Day 26-36)
Week 8 (Day 57)	±7 days (Day 50-64)	-7/+14 days (Day 50-71)
Week 12 (Day 85)	±7 days (Day 82-88)	-7/+21 days (Day 82-106)
Week 18 (Day 127)	±7 days (Day 120-134)	-7/+21 days (Day 120-148)
Week 24 (Day 169)	±7 days (Day 162-176)	±7 days (Day 162-176)
Week 26 (Day 183)	±3 days (Day 180-186)	±3 days (Day 180-186)
Week 28 (Day 197)	±3 days (Day 194-200)	-3/+21 days (Day 194-218)
Week 34 (Day 239)	±7 days (Day 232-246)	-7/+21 days (Day 232-260)
Week 40 (Day 281)	±7 days (Day 274-288)	-7/+30 days (Day 274-311)
Week 48 (Day 337) c	±7 days (Day 330-344)	-7/+30 days (Day 330-367)

a. These are the same as the windows in the protocol [Schedule of Activities](#).

b. Laboratory results must be received and reviewed by the investigator within 14 days after they are collected to determine eligibility to continue dosing. In addition, laboratory test results from the previous visit must be available and reviewed by the investigator prior to shipping investigational product at the current visit.

c. If subject is rolling over into B7981032, labs must be collected prior to enrollment in B7981032.

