### 1.7. Summary of Benefit/Risk Assessment

In the Phase 2a proof-of-concept Study B7931005 in adult patients with AA, PF-06651600 met its primary endpoint of improvement in SALT score relative to placebo at Week 24. PF-06651600 appeared generally safe and well tolerated as suggested by adverse event (AE) number and profile. Reductions in platelet counts and lymphocyte counts were observed during treatment with 200 mg QD but were not considered clinically meaningful and improved after switching to 50 mg QD during the maintenance phase of the study. PF-06651600 is an immunomodulator and, as such, can be associated with the potential risk of infection (including serious infection), opportunistic infections, and viral reactivation. The risk of infection will be monitored and evaluated in longer term studies of PF-06651600.

These preliminary clinical data indicate that PF-06651600 has a favorable benefit: risk profile and provides meaningful clinical benefit in a serious disease with no approved treatment options. The benefit of evaluating PF-06651600 in adolescents is additionally supported by prevalence of AA in adolescents, the significant psychological burden of disease in this population, and a recent case series suggesting that extended duration of AA appears to increase likelihood of being refractory to off-label tofacitinib treatment.

It is not known whether PF-06651600 is secreted into human milk. In animals, PF-06651600 was associated with fetal changes in bones and some internal organs, and lower fetal body weights. Because of the investigational nature of PF-06651600, it should not be administered to pregnant women, breastfeeding women, or fertile women of childbearing potential who are unwilling or unable to use contraception as defined in the study protocol. PF-06651600 is not likely to transfer to a partner through semen at pharmacologically relevant levels.

Additional information for this compound may be found in the single reference safety document (SRSD), which for this study is the Investigator's Brochure (IB).

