## 6. STUDY PROCEDURES

Refer to the [Schedule of Activities](#) for a detailed list of study procedures as they should be conducted at each respective visit. Visit windows are based on Day 1 visit.

Subjects are required to fast for at least **8 hours** prior to all visits that include fasting lipid profile panel testing. During the fasting period, subjects should refrain from all food and liquids (water and medications other than investigational product are permitted).

To assure consistency and reduce variability, visits should occur at approximately the same time of day throughout the study. Subjects should be encouraged to attend visits in the morning and prior to the subject's dosing of investigational product as subjects will receive their dose at the clinic during their study visit.

Urine pregnancy test must be performed at each visit (and must be negative) prior to dosing with the investigational product for female subjects of childbearing potential through end of study (EOS). In addition to urine pregnancy tests performed at each study visit, sites in VHP countries in the EMA should instruct female subjects of childbearing potential to perform a urine pregnancy test at home between the Week 40 and 48 visits (at approximately Week 44). In addition, the investigator or designee will instruct the subject to contact the site immediately if the urine pregnancy test result is positive or cannot be confirmed as negative. The list of VHP countries participating in the protocol can be found in [Section 4](#).

The patient reported outcome assessments should be completed before the other evaluations or treatments at the clinical visits whenever it is possible. Vital signs and electrocardiograms (ECGs) should be performed before any laboratory blood collection. The CGIS-AA should be completed after other clinical assessments of AA (ie, SALT, EBA, ELA, and assessment of fingernails affected by AA), whenever it is possible. All other evaluations (unless noted otherwise) do not need to be performed in any specific order.

Refer to [Appendix 3](#) for guidelines on subject safety monitoring and discontinuation.

### 6.1. Screening, Visit 1

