### **7.2. Pregnancy Testing**

Pregnancy tests are required to be done (if applicable) as specified in the [Schedule of Activities](#).

Pregnancy tests must have a sensitivity of at least 25 mIU/mL. Pregnancy tests should be urine pregnancy tests. In the event that urine pregnancy tests are not permitted at an institution, serum pregnancy tests can be utilized. Pregnancy tests will be performed in WOCBP at the times listed in the [Schedule of Activities](#). Following a negative pregnancy

test result at screening, appropriate contraception must be verified, and a second negative pregnancy test result will be required at the baseline visit prior the subject receiving the investigational product. Pregnancy tests will also be done whenever 1 menstrual cycle is missed during the active treatment period (or when potential pregnancy is otherwise suspected) and at the end of the study. Pregnancy tests may also be repeated if requested by institutional review boards (IRBs)/ethics committees (ECs) or if required by local regulations. If a urine test cannot be confirmed as negative (eg, an ambiguous result), a serum pregnancy test is required. In such cases, the subject must be excluded if the serum pregnancy result is positive. In the case of a positive confirmed pregnancy, the subject will be withdrawn from administration of investigational product but may remain in the study for follow-up.

In addition to urine pregnancy tests performed at each study visit, sites in VHP countries in the EMA should instruct female subjects of childbearing potential to perform a urine pregnancy test at home between the Week 40 and 48 visits (at approximately Week 44). In addition, the investigator or designee will instruct the subject to contact the site immediately if the urine pregnancy test result is positive or cannot be confirmed as negative. The list of VHP countries participating in the protocol can be found in [Section 4](#).

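### Appendix 6.3 allows a home pregnancy kit at 25 IU/mL where Section 7.2 requires 25 mIU/mL: probably a dropped m, but wrong by a factor of 1000 in a test that gates drug shipment

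*Protocol*

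**What the plan says.** Section 7.2 of the protocol states the general rule: "Pregnancy tests must have a sensitivity of at least 25 mIU/mL". It makes no exception for tests done at home. The same section asks sites in the VHP countries to have women of childbearing potential test themselves at home at about Week 44, so home testing is within its scope.

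Appendix 6.3 covers public emergencies, including COVID-19. Its home-testing provision begins "If a subject requiring pregnancy testing cannot visit a local laboratory for pregnancy testing" and continues that "a home urine pregnancy testing kit with a sensitivity of at least 25 IU/mL may be used", provided this complies with local regulatory requirements. The subject may report the result during the remote visit. The appendix then makes the result a condition of supply: "The urine pregnancy test result must be available prior to dispensing or shipping investigational product to a subject". Section 6 adds the general requirement: "Urine pregnancy test must be performed at each visit (and must be negative) prior to dosing with the investigational product".

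Appendices 6.2 (telehealth) and 6.5 (home health visits) send sites to both Section 7.2 and Appendix 6.3 for pregnancy testing.

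**The concern.** The two sections give the same numeral in units that differ by three orders of magnitude, and the protocol does not say which figure governs. Appendix 6 presents itself as the set of measures to follow during an emergency, and it applies for the duration of the COVID-19 pandemic. A site could therefore reasonably take its kit-specific figure as the operative one.

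What is at stake is reproductive safety. Section 1.7 reports: "In animals, PF-06651600 was associated with fetal changes in bones and some internal organs, and lower fetal body weights". It also says the drug should not be given to pregnant women. An insensitive kit fails by giving a false negative, and the serum back-ups are not designed to catch that. Appendix 3.1 acts on a positive result: "In case of positive urine pregnancy test, the subject will have study drug interrupted and a serum sample collected on the same day". Section 7.2 acts on a doubtful one: "If a urine test cannot be confirmed as negative (eg, an ambiguous result), a serum pregnancy test is required". A clear but false negative triggers neither, and drug can then be shipped.

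**Working it through.** The plan derives no figure here, so there is nothing to reproduce. The check is a unit conversion and a comparison of the provisions.

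**Inputs**
- Section 7.2: 25 mIU/mL.
- Appendix 6.3: 25 IU/mL.
- Conversion: 1 IU = 1000 mIU.

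**Size of the discrepancy**
- Appendix 6.3 in the units of Section 7.2: 25 × 1000 = 25,000 mIU/mL.
- Ratio to the Section 7.2 limit: 25,000 / 25 = 1000.

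**Which kits are affected**

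| Kit detection limit | Meets Section 7.2 | Meets Appendix 6.3 as printed |
|---|---|---|
| 25 mIU/mL or lower | yes | yes |
| above 25 and up to 25,000 mIU/mL | no | yes |
| above 25,000 mIU/mL | no | no |

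The conflict runs one way. A kit that meets Section 7.2 satisfies both provisions; the middle row passes Appendix 6.3 alone.

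**How often the fallback could gate drug supply**
- Table 8 in Appendix 6.3 lists the visits that can be remote: Weeks 2, 4, 8, 12, 18, 24, 26, 28, 34, 40 and 48, which is 11.
- Sections 6.2.2 to 6.2.11 (Weeks 2 to 40) each include dispensing. Section 6.2.12 (Week 48) does not.
- Upper bound: 11 − 1 = 10 visits per woman of childbearing potential.

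The extracted Schedule of Activities appears to carry one further dispensing mark, at Week 48. The count is context only, and the unit conflict does not depend on it.

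**The case against.** The strongest reply is that Section 7.2 already settles the matter. It is a general requirement, whereas Appendix 6.3 only permits, and Section 7.2 plainly reaches home tests because it includes the Week 44 home test. A site that follows both provisions has one compliant choice, a 25 mIU/mL kit. The appendix also requires compliance with local regulations. On this view the 1000-fold figure measures a missing prefix that nobody intended, not a risk, and no document shows that kits in the gap exist or would be used.

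The bound of 10 visits is also loose:
- Appendix 6.1 requires that Week 2 and Week 4 safety laboratory tests be expected at the site or at an alternative laboratory before a subject is enrolled under these measures.
- Appendix 6.3 requires drug to be withheld if laboratory samples are not collected within the extended window.
- Appendix 6.4 bars shipment until the previous visit's laboratory results have been reviewed.
- Appendix 6.5 offers pregnancy testing at a home health visit.
- The measures are expected to end when normal circumstances return.

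All of this limits the practical effect, and it is right that this is a unit inconsistency, not a failed calculation. It does not remove the conflict. A protocol should not depend on sites noticing that two cross-referenced sections disagree, particularly when the subject performs the test and may report the result remotely. A character lost in reading the PDF cannot be wholly excluded, but nothing on the page suggests it, and the source can be checked in moments.

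**Conclusion.** The concern holds. Both figures stand in current text, and the home-kit limit in Appendix 6.3 is 1000 times looser than Section 7.2 allows, with no justification given. A dropped m is the most plausible explanation; there is no sign of a deliberate relaxation.

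The error is in the acceptance limit of a safety test on which drug supply depends, so it should be corrected. It falls short of critical because the kit is a conditional fallback and other protections remain, notably contraception checks and pregnancy testing after a missed menstrual cycle. The actual exposure is unknown and may be small, since the documents contain no kit data. Sample size, alpha, power and the efficacy analyses are untouched.

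**What to change.** In Appendix 6.3, change the home-kit sensitivity from 25 IU/mL to 25 mIU/mL so that it matches Section 7.2. Send sites an administrative letter stating that 25 mIU/mL applies to home kits.

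The cost is one unit correction and one letter, with no change to design or analysis. There is precedent: the Document History shows that a platelet exclusion threshold (Amendment 1), and the PPD wording and a hemoglobin monitoring criterion (Amendment 2), were corrected as typographic errors and communicated to sites by administrative letter.
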